#### **6.3.8.6 Laboratory Evaluations**

If subjects cannot attend clinic visits for laboratory evaluations, they are allowed to use local laboratories, or to have site staff visit them at their homes for blood draws.

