5.3 Analysis Visit Windows

In general, the open-label Baseline assessment will be defined as the last non-missing assessment, including those from repeated and unscheduled measurements, before or on the first open-label dose date. Exceptions to this definition will be handled on a case by case basis.

Efficacy and safety assessments will be summarized by analysis visit as presented in Table 1 below.

Table 1 Analysis Visit Windows

Open-label (OL) Analysis Visit Name	Target Study Day¹	Study Day Interval
OL Baseline	1	≤1 (based on the first OL dose date)
OL Week 2	15	2 to 21
OL Week 4	29	22 to 42
OL Week 8	57	43 to 70
OL Week 12	85	71 to 98
OL Week 16	113	99 to 154
OL Week 28	197	155 to 238
OL Week 40	281	239 to 322
OL Week 52	365	323 to 379
OL Follow-up	395	380 – maximum

¹ If the assessment date ≥ first OL dose date, study day = assessment date - first OL dose date + 1, otherwise study day = assessment date – first OL dose. Study day 1 is the first OL dose date.

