5.3.1 Unscheduled Assessments

Both scheduled and unscheduled assessments, including early termination visits and remote visits, will be considered for planned timepoint summaries. All assessments will be presented in data listings.

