5.3.2 Multiple Measurements within Visit Windows

If more than one assessment falls within a given window then the assessment closest to the target study day will be selected for the by-visit summaries. If two assessments are equidistant from the target day then the chronologically last assessment will be used for summary. Exceptions may be made for incomplete assessments, in which case, more complete assessments may be given priority. Details are provided in a separate programming conventions document.

For safety summaries where the most extreme values should be selected, e.g. overall post-baseline minimum, overall post-baseline maximum, and potentially clinically important values for overall post-Baseline summaries, all non-missing post-Baseline values should be considered, regardless of whether the value is selected for the by-visit summaries. All results will be presented in data listings.

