14.2 Clinical Laboratory Variables

Clinical laboratory tests are performed at Baseline, Week 12, and Week 52 (EOT/ET).

In general, laboratory test results are from a central laboratory. Due to COVID-19 disruptions it is possible that some test results may be collected from a local laboratory. A separate eCRF will capture local laboratory results in order to facilitate medical monitoring of subject safety. Local laboratory results will not be included in any summary data analysis; they will, however, be included in separate data listings. All results (central and local) will be displayed in Système International [SI] units. It is encouraged, but not required, that clinical labs be completed under fasting conditions. The listings will include date and study day of collection. Out of range values will be flagged in the data listings.

- Hematology tests
 - Complete blood count (CBC) including:
 - White blood cell (WBC) count
 - Complete differential (relative and absolute)
 - Hematocrit (Hct), hemoglobin (Hgb), red blood cells (RBC), platelets
 - Reticulocyte count
- Clinical chemistry serum tests
 - Sodium (Na), potassium (K), chloride (Cl), phosphorus (P), calcium (Ca), carbon dioxide (CO₂), blood urea nitrogen (BUN), creatinine (Cr), uric acid
 - Alanine aminotransferase (ALT), aspartate aminotransferase (AST), gamma-glutamyl transpeptidase (GGT), alkaline phosphatase (ALP), total bilirubin (TBIL), lactate dehydrogenase (LDH)
 - Glucose
 - Albumin (ALB), total protein
 - Prolactin
 - Creatine kinase (CK)/creatinine phosphokinase (CPK)
 - Lipid panel
 - Total cholesterol, high-density lipoprotein (HDL)-cholesterol, triglycerides, low-density lipoprotein(LDL)-cholesterol, very low density lipoprotein cholesterol
- Urinalysis
 - Blood, RBCs, WBCs, protein, glucose, ketones, specific gravity, pH

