Sodium	mEq/L	≤125	≥155	mmol/L	≤125	≥155
Potassium	mEq/L	≤3.0	≥5.5	mmol/L	≤3.0	≥5.5
Calcium, total	mg/dL	<8.0	>11.0	mmol/L	<2.0	>2.75
Lactate Dehydrogenase (LDH)	U/L	No lower limit	≥3 X ULN	U/L	No lower limit	≥3 X ULN
Alkaline Phosphatase	U/L	No lower limit	≥3 X ULN	U/L	No lower limit	≥3 X ULN
Uric acid (male)	mg/dL	No lower limit	≥10.5	umol/L	No lower limit	≥624.75
Uric acid (female)	mg/dL	No lower limit	≥8.5	umol/L	No lower limit	≥505.75
Albumin	g/dL	≤2.6	≥6.0	g/L	≤26	≥60
Total Protein	g/dL	≤5.0	≥10.0	g/L	≤50	≥100
Chloride	mEq/L	≤85	≥120	mmol/L	≤85	≥120
Glucose (random)	mg/dL	≤45.1	≥200.0	mmol/L	≤2.48	≥11
Serum Creatinine	mg/dL	Not Applicable	>1.5 ULN	umol/L	Not Applicable	>1.5 ULN
Triglycerides	mg/dL	Not Applicable	>300	mmol/L	Not Applicable	>3.39
Gamma-Glutamyl Transferase (GGT)	U/L	Not Applicable	≥3 ULN	U/L	Not Applicable	≥3 ULN

Table 3 Criteria for Potentially Clinically Important Laboratory Values - Urinalysis

Urinalysis (qualitative dipstick)	Low PCI Criteria	High PCI Criteria
Blood (occult blood)	Not Applicable	≥ Moderate
Protein	Not Applicable	≥ 100 mg/dL
Glucose	Not Applicable	≥ 500 mg/dL

The number and percentage of subjects with the shift from baseline, both double-blind and open-label, to weeks 12 and 52 that meet the following criteria in the blood lipid parameters and glucose will be summarized by fasting status (fasting vs. non-fasting):

- Total Cholesterol – (<200 mg/dL to ≥240 mg/dL)
- Triglycerides – (<150 mg/dL to ≥200 mg/dL)
- LDL Cholesterol – (<100 mg/dL to ≥160 mg/dL)
- HDL Cholesterol – (≥40 mg/dL to <40 mg/dL)
- Glucose fasting – (<100 mg/dL to ≥126 mg/dL)
- Glucose non-fasting – (<140 mg/dL to ≥140 mg/dL)
- Glucose fasting – (≥100 mg/dL and <126 mg/dL to ≥126 mg/dL)
- Glucose non-fasting - (≥140mg/dL and <200 mg/dL to ≥200 mg/dL)

The pregnancy results (positive or negative) for female subjects will be presented in a listing.

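### The lipid and glucose category-shift table has only Week 12 and Week 52 rows, so early-termination values outside those two day windows are not counted against its cut-points (minor)

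*SAP*

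**What the plan says.** The table at issue is the last shift summary in SAP 14.2. It covers eight criteria: four for lipids (total cholesterol, triglycerides, LDL, HDL) and four for glucose, all presented by fasting status. Its timepoints are set in one phrase: "The number and percentage of subjects with the shift from baseline, both double-blind and open-label, to weeks 12 and 52". No overall, last-value or early-termination row is mentioned.

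Laboratory samples are scheduled at Baseline, Week 12 and the Week 52 visit. That last visit doubles as the early-termination (ET) visit (SAP 14.2; Protocol Table 6–1).

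Two rules in SAP 5.3 decide where a value is reported. The first is "Efficacy and safety assessments will be summarized by analysis visit as presented in Table 1 below", and Table 1 there is defined by study day. The second, in SAP 5.3.1, is "Both scheduled and unscheduled assessments, including early termination visits and remote visits, will be considered for planned timepoint summaries". Neither rule moves an ET value to Week 52 regardless of its day.

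Local results are a separate matter. Protocol 6.3.8.6 says "If subjects cannot attend clinic visits for laboratory evaluations, they are allowed to use local laboratories", while SAP 14.2 says "Local laboratory results will not be included in any summary data analysis; they will, however, be included in separate data listings". The point below therefore concerns central-laboratory values only.

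SAP 3.6 records that the study was stopped early and that the subjects still in it were discontinued.

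**The concern.** In a study stopped early, many last visits will be ET visits, and these need not fall near Week 12 or Week 52. For some subjects the ET draw may be the last metabolic measurement, or the only one after Baseline. A table limited to two day windows does not count such a draw unless it happens to fall inside one of them.

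At stake is the count of subjects who crossed these lipid and glucose cut-points on long-term treatment. A subject who crossed one between the two windows, or before the first, would not appear as a shift in the only table that uses these cut-points.

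**Working it through.** **Step 1: where an ET draw lands.** Windows are from SAP 5.3, Table 1; length = last day − first day + 1.

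| Study day | Analysis visit | Days | Row in this table |
|---|---|---|---|
| 2–21 | Week 2 | 20 | none |
| 22–42 | Week 4 | 21 | none |
| 43–70 | Week 8 | 28 | none |
| 71–98 | Week 12 | 28 | Week 12 |
| 99–154 | Week 16 | 56 | none |
| 155–238 | Week 28 | 84 | none |
| 239–322 | Week 40 | 84 | none |
| 323–379 | Week 52 | 57 | Week 52 |
| 380 onward | Follow-up | open | none |

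Days 2–379 number 378. Uncovered before Week 12: 20 + 21 + 28 = 69. Uncovered between the two windows: 56 + 84 + 84 = 224. Total 69 + 224 = 293, and the check 378 − 28 − 57 = 293 agrees. Day 380 onward is also uncovered. These are counts of days, not of subjects.

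**Step 2: what this means for a subject.**

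- Only post-Baseline draw on days 2–70: absent from the table.
- Left on days 99–322 with a Week 12 draw in window: present in the Week 12 row, but a shift first seen at the ET draw is not counted.
- Left on days 99–322 without a Week 12 draw in window: absent from the table.
- Final draw on day 380 or later: not in the Week 52 row.

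**Step 3: where the same values are still used.** SAP 14.2 summarises overall minimum, maximum and last post-Baseline values. It also gives normal-range shifts to the overall minimum and maximum. For glucose and the lipid panel, both are given by fasting status. The overall counts of potentially clinically important (PCI) values use every post-Baseline value, including unscheduled and out-of-window ones. SAP 5 lists all data.

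**Step 4: do those summaries apply the same cut-points?** Normal-range shifts use low, normal and high, not these category pairs. The PCI limits in SAP Table 2 compare as follows (mg/dL):

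| Parameter | Shift end-point | High PCI limit |
|---|---|---|
| Total cholesterol | ≥240 | none |
| LDL | ≥160 | none |
| HDL | <40 | none (no low limit either) |
| Triglycerides | ≥200 | >300 |
| Glucose, fasting | ≥126 | ≥200 (random) |
| Glucose, non-fasting | ≥140 and ≥200 | ≥200 (random) |

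Only non-fasting glucose ≥200 coincides, and there the PCI count does not use this table's starting category.

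**The case against.** **Nothing planned in the protocol is lost.** The laboratory endpoint in Protocol 2.2.1 is PCI values. Protocol 9.5.2 asks for a summary across all post-Baseline timepoints only for those, and SAP 14.2 delivers it. The category-shift table is an addition made in the SAP, and nothing is tested. All of this stands, and it is why the point is minor. A reader might infer that ET laboratory data are discarded; Step 3 shows that they are not.

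**The schedule labels the last visit Week 52 (EOT/ET), which could mean that ET values count as Week 52.** That label says when samples are drawn; SAP 5.3 says how they are summarised, and it goes by day. If the sponsor does intend such a mapping, the Week 52 row would mix exposure durations under a Week 52 name, and the SAP should say so.

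**Other categorical tables also lack an overall row.** True of urinalysis categories, responder and remission rates, and sexual dysfunction. But the last three are shown at all eight post-Baseline visits, so an ET value has a column. Urinalysis shares the two-visit gap.

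**The detail may sit elsewhere.** Table specifications are in a separate document (SAP 1), and on choosing among several values in a window SAP 5.3.2 says "Details are provided in a separate programming conventions document". So the programmed handling cannot be confirmed from what is public. This stands as a limit on certainty.

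Three stronger readings are tempting and are not supported:

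- *The table has no denominator.* SAP 5.1 sets a general rule (subjects with non-missing values), and SAP 14.2 gives a by-visit shift rule (non-missing at Baseline and at that visit).
- *The four lipid criteria are ambiguous because they carry no fasting label.* SAP 14.2 does say "It is encouraged, but not required, that clinical labs be completed under fasting conditions", but the sentence introducing the table stratifies all eight criteria by fasting status. Whether the baseline and follow-up samples must match is unstated, as it is for the normal-range shift tables. It is not a defect particular to this table.
- *Most subjects are missed because 293 of 378 days are uncovered.* Days are not subjects, and on 224 of those 293 days a subject has passed the Week 12 visit and should normally already be in that row.

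**Conclusion.** The point holds as a minor one. As written, the table does not count central-laboratory ET values on days 2–70, days 99–322 or day 380 onward against its cut-points. The consequence is greatest for total, LDL and HDL cholesterol, which have no PCI limit. The number of subjects affected cannot be computed, since the documents give no distribution of ET dates.

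This rests on two assumptions: that the Table 1 windows apply to this table as SAP 5.3 states, and that no separate specification reassigns ET values. The effect is confined to one descriptive table, and the underlying values remain in the listings and in the other laboratory summaries.

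**What to change.** Keep the Week 12 and Week 52 rows exactly as they are and add one overall post-Baseline row:

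- Use either the last value or any value, and state which. Any value matches the PCI counts but gives subjects with more draws more chances to qualify; last value uses one result per subject.
- Give it for both the double-blind and the open-label baseline, by fasting status as the table already provides.
- Include all post-Baseline central-laboratory values: ET, unscheduled and out of window.
- Use the denominator that SAP 14.2 already sets for overall shifts: subjects with a non-missing Baseline and at least one post-Baseline value for the parameter.
- Label the row as mixing exposure durations.

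The cost is a sentence or two in the SAP and minor programming, with no new data. The downside is the mixed exposure in the new row. Local-laboratory ET results would stay in the listings only, so the change does not recover them. No new denominator or fasting-match rule is needed for the existing rows.

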Clinical laboratory values reported as continuous values for hematology, chemistry and urinalysis will be summarized using descriptive statistics at Baseline and scheduled post-Baseline visits. The change from Baseline values will also be summarized at scheduled post-Baseline visits. The overall minimum, maximum and last post-Baseline observed and change from Baseline values will also be summarized. For hemoglobin, hematocrit and uric acid, the above summaries will be presented for each gender as well as for both genders combined. For urinalysis with categorical results, the number and percentage of subjects will be tabulated by category at Baseline and scheduled post-Baseline visits, and the denominator is the number of subjects with non-missing values for the given parameter and visit. For glucose and lipid panel, the summary table will also be presented by fasting status (fasting vs. non-fasting).

Laboratory values will also be summarized in shift tables to determine the number and percentage of subjects with values classified as below (low), within (normal), or above (high) normal ranges at scheduled post-Baseline visits relative to the same classification at the Baseline visit. The shifts from Baseline to overall post-Baseline minimum and overall post-Baseline maximum will also be presented. For the by-visit shift summary, the denominator is the number of subjects with non-missing values at Baseline and the given visit for the given

parameter. For the summaries of shift from Baseline to the overall post-Baseline minimum or maximum, the denominator is the number of subjects with non-missing Baseline and at least 1 post-Baseline value for the given parameter. For hemoglobin, hematocrit and uric acid, the shift summaries will be presented for each gender as well as for both genders combined. For glucose and lipid panel, the shift table will be presented by fasting status (fasting vs. non-fasting).

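### The LDL, total cholesterol and triglyceride shift rows leave out borderline Baselines, although the glucose rows include them, so many new high values are not counted there

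*SAP*

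**What the plan says.** SAP 14.2 (Clinical Laboratory Variables) ends with a list of category shifts for lipids and glucose. They are counted from the double-blind and the open-label Baseline to Weeks 12 and 52, by fasting status. The lipid rows are:

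- one upward row for LDL, with cuts 60 mg/dL apart: "LDL Cholesterol – (<100 mg/dL to ≥160 mg/dL";
- one upward row for total cholesterol, with cuts 40 mg/dL apart: "Total Cholesterol – (<200 mg/dL to ≥240 mg/dL";
- one upward row for triglycerides, from below 150 to at least 200 mg/dL;
- one downward row for HDL, with a single cut: "HDL Cholesterol – (≥40 mg/dL to <40 mg/dL".

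For glucose, the list also gives intermediate Baselines a row of their own: for fasting samples "Glucose fasting – (≥100 mg/dL and <126 mg/dL to ≥126 mg/dL", with a matching non-fasting row from 140 to <200 up to at least 200 mg/dL.

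No denominator is stated for this list. The general rule in SAP 5.1 is all subjects with non-missing values.

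SAP 14.2 plans other lipid displays as well: observed values and change from Baseline by visit; the overall minimum, maximum and last post-Baseline values; and shifts against the laboratory's normal range. On the last, the SAP states: "Laboratory values will also be summarized in shift tables to determine the number and percentage of subjects". The classes are low, normal and high, and lipids are split into fasting and non-fasting samples. SAP Table 2 has a potentially clinically important (PCI) criterion for triglycerides (>300 mg/dL) but none for total, LDL or HDL cholesterol.

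**The concern.** Between the two cuts of each upward lipid row lies a Baseline band that no row covers: LDL 100 to <160, total cholesterol 200 to <240, triglycerides 150 to <200 mg/dL. A rise in LDL from 105 to 200 is not counted, nor is one from 159 to 250. To be counted, a value must start below the lower cut and rise by more than 60 mg/dL (LDL), 40 mg/dL (total cholesterol) or 50 mg/dL (triglycerides).

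The list is uneven. The first fasting glucose row (<100 to ≥126) has the same kind of gap, and the second row fills it. No reason is given for not doing this for three of the four lipids.

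Under the SAP 5.1 rule, borderline subjects would also sit in the denominator without being able to enter the numerator, which lowers the percentage further.

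At stake is the reading of a planned safety table. Safety is the primary objective, and Protocol 1.2 describes the drug as an atypical antipsychotic. A reader who sees an LDL row at or near zero may take it that hardly anyone newly reached 160 mg/dL, when the row could not have shown most of those who did.

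**Working it through.** **No figure to reproduce.** The documents give no lipid mean, SD, within-subject correlation or expected shift rate. The gap follows from the cuts alone; its size needs assumptions.

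**Inputs from SAP 14.2.** Lower and high cuts *l* and *h* (mg/dL): LDL 100 and 160; total cholesterol 200 and 240; triglycerides 150 and 200.

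**Assumed inputs (not in the documents).**

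- LDL: mean 100-130, SD 30-35.
- Total cholesterol: mean 180-200, SD 35-40.
- Triglycerides: median 100-130, log-SD 0.45-0.55.
- Mean change: 0 or +10 mg/dL (+10% for triglycerides).
- Correlation *r* of Baseline and post-Baseline values: 0.4-0.9, with 0.6-0.8 as the main range.

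**Formula.** Baseline X and post-Baseline Y are bivariate normal with equal SD (log scale for triglycerides).

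Share counted = P(X < *l*, Y ≥ *h*) / P(X < *h*, Y ≥ *h*). Share missed = 1 − share counted.

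**One case in full: LDL, mean 115, SD 33, r = 0.7, no mean change.**

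- Standardised cuts: (100 − 115)/33 = −0.455 and (160 − 115)/33 = 1.364.
- Baseline below 100: 32.5% of subjects. Baseline in the skipped band: 58.9%.
- P(X < 160, Y ≥ 160) = 0.0475. P(X < 100, Y ≥ 160) = 0.0009.
- Share counted = 0.0197 (from unrounded values), so 98.0% are missed.

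**Mid-range cases at r = 0.7, no mean change, per 420 paired results.** 420 is the planned number and so an upper bound: SAP 3.5 says that the actual number will be lower.

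| Parameter | Assumed Baseline | In skipped band | New highs | Counted by the row | Missed |
|---|---|---|---|---|---|
| LDL | mean 115, SD 33 | 58.9% | 19.9 | 0.4 | 98.0% |
| Total cholesterol | mean 190, SD 38 | 30.2% | 21.3 | 3.9 | 81.8% |
| Triglycerides | median 115, log-SD 0.5 | 16.3% | 27.9 | 12.5 | 55.2% |

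**Full range of assumptions: percentage of new highs missed, minimum to maximum (median).**

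| r | LDL | Total cholesterol | Triglycerides |
|---|---|---|---|
| 0.4 | 75.3-93.7 (85.7) | 48.1-65.6 (56.4) | 27.4-41.1 (33.6) |
| 0.5 | 82.1-96.1 (90.3) | 55.2-72.1 (63.4) | 32.1-46.7 (38.7) |
| 0.6 | 88.5-98.0 (94.5) | 63.2-79.2 (71.2) | 37.9-53.4 (44.7) |
| 0.7 | 94.2-99.3 (97.6) | 72.6-86.7 (79.9) | 45.5-61.8 (53.1) |
| 0.8 | 98.3-99.9 (99.5) | 83.6-94.1 (89.3) | 56.3-73.1 (64.3) |
| 0.9 | at least 99.9 | 95.4-99.3 (97.9) | 73.7-88.8 (81.4) |

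**How much the normal-range shift table recovers.** The laboratory's upper limit is not given. If it lies inside the LDL band, a subject who starts below the limit and reaches 160 appears there as normal to high. With the LDL case above (mean 115, SD 33, no mean change, r = 0.6-0.8) and the assumed limit in place of *l*, a limit of 130 mg/dL takes in about 15-35% of new values ≥160, and a limit of 150 about 62-77%. If instead the change is independent of Baseline (LDL mean 112, SD 33, change SD 18-28, no mean change), the figures are about 9-27% and 57-74%. In either model these subjects are mixed with those who passed the limit but stayed below 160.

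**After the fix.** The existing row and the added row together cover every Baseline below the high cut, so all new highs are counted by construction.

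**The case against.** The strongest case against is that lipid worsening is shown elsewhere. A general rise in LDL would appear in the change-from-Baseline and overall-maximum summaries, and the normal-range shift table would show part of the movement within the borderline bands. Laboratory values are exploratory (Protocol 2.2.1), the primary endpoint is TEAEs (Protocol 2.1.1), nothing is tested and no decision rule uses these rows. A normal-to-high row also has a use of its own: it isolates large moves. A borderline-to-high row pools 159 to 160 with 101 to 160 and will fill partly through ordinary variation; the 19.9 new high LDL values above arise with no mean change at all.

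Much of this stands, and it rules out several stronger readings that a reader might infer:

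- *That all the lipid rows have the gap.* The HDL row does not: its two categories meet at 40 mg/dL.
- *That the triglyceride row misses most new highs.* That depends on the correlation. The median case misses more than half at r = 0.7 but 44.7% at r = 0.6.
- *That the normal-range shift table helps only if the laboratory's limit lies above the bands.* A limit inside a band also helps; the overlap is unknown, not nil.
- *That the trial would report no lipid signal.* The other summaries make that too strong. The risk is a misreading of these rows.

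What the objection does not remove is that no other planned display counts subjects newly at ≥160, ≥240 or ≥200 mg/dL, the high cuts that the SAP itself chose. Means and maxima do not give that number, the normal-range table uses other limits, and the triglyceride PCI criterion starts above 300 mg/dL.

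**Conclusion.** The point holds for LDL, total cholesterol and triglycerides. That these rows omit borderline Baselines, unlike the glucose rows, is plain from SAP 14.2 and needs no assumption.

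The size is conditional on Baseline distributions that the documents do not give. At a correlation of 0.6-0.8, the LDL row misses about 90% or more of new highs (88.5% at the least favourable setting), the total cholesterol row about 60-95%, and the triglyceride row about 40-75%. At 0.4-0.5 the shares fall to about 75-96%, 48-72% and 27-47%. The LDL conclusion is robust, the total cholesterol conclusion nearly so, and the triglyceride one is not robust as a majority claim.

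The consequence is moderate: a descriptive safety table that can mislead if read alone, partly offset by other displays and cheap to repair.

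**What to change.** Keep the existing rows and add three to the SAP 14.2 list, for both Baselines, both weeks and both fasting strata:

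- total cholesterol ≥200 and <240 to ≥240 mg/dL;
- triglycerides ≥150 and <200 to ≥200 mg/dL;
- LDL ≥100 and <160 to ≥160 mg/dL.

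State the denominator of each added row: subjects whose Baseline lies in that row's band and who have a value at the visit.

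Add a note that some borderline-to-high shifts will be ordinary variation, which a single-arm study cannot separate from a drug effect, so the rows are to be read beside the change-from-Baseline summaries.

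The cost is three rows in a planned table, programmed from data already collected. The downside is that variation in the counts, together with small cells once the rows are split by fasting status in a study that stopped early.
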